4 SELECTION AND ENROLLMENT OF PARTICIPANTS

Participants will be eligible to enroll in the rTMS study if, based on screening assessments, they have a clinical diagnosis of amnestic Mild Cognitive Impairment (aMCI) (Albert et al., 2011; R. C. Petersen, 2004) and they meet all of the following inclusion and exclusion criteria:

4.1 Inclusion Criteria

1. Age 55 – 90 years inclusive;
2. Diagnosed with amnestic Mild Cognitive Impairment (aMCI);
3. Stable medications (including any dementia-related meds) for at least 4 weeks prior to Baseline;
4. Geriatric Depression Scale score less than 6;
5. Ability to obtain a motor threshold, determined during the screening process;
6. Study partner available; living situation enables attendance at clinic visits;
7. Visual and auditory acuity adequate for neuropsychological testing;
8. Good general health with no diseases expected to interfere with the study, as determined by the referring Memory Clinic Physician or the rTMS Study Physician;
9. Participant is not pregnant or of childbearing potential (i.e. women must be 2 years post-menopausal or surgically sterile);
10. Modified Hachinski Ischemic score less than or equal to 4;
11. Agree to DNA extraction for single nucleotide polymorphism (SNP) genotyping;
12. Able to understand study procedures and comply with them for the entire length of the study.

4.2 Exclusion Criteria

A candidate will be excluded from the study if he or she meets any of the following exclusion criteria at Screening or Baseline:

1. Prior exposure to rTMS within the past 12 months;
2. Magnetic field safety concern such as a cardiac pacemaker, cochlear implant, implanted device in the brain (deep brain stimulation), or metal fragments or foreign objects in the eyes, skin or body;
3. Any significant neurological disease other than suspected incipient Alzheimer's disease;
4. Unstable cardiac disease or recent (< 3 months previous) myocardial infarction. Any significant systemic illness or unstable medical condition that could lead to difficulty with protocol adherence;
5. History of epilepsy or repetitive seizures, as determined by patient report or chart review;
6. History of a medical condition or current use/abuse of medications and substances that increase the risk of a seizure, specifically:

- Traumatic brain injury within 2 months that would increase the risk for seizure;
- Unable to safely withdraw, at least 4 weeks prior to Baseline, from medications that substantially increase the risk of having seizures (for example, theophylline, clozapine, and methylphenidate). See Appendix III. "List of Exclusionary Medications."
- Current or past history of a mass lesion, cerebral infarct, or other non-cognitive active neurological disease that would increase the risk for seizure.
- Stimulant abuse within the previous 90 days. Cocaine and abuse of amphetamine and methylphenidate are associated with an increased risk of seizures;

7. Major depression or bipolar disorder (DSM-IV) within the past 1 year, or psychotic features within the last 3 months that could lead to difficulty w/protocol adherence;
8. Taking sedative hypnotics or medications with anti-cholinergic properties and unable to withdraw at least 4 weeks prior to Baseline;
9. Current alcohol or substance abuse (not including caffeine or nicotine) within the past 1 year, as determined by chart review, participant or study partner report, or greater than "moderate" alcohol use defined by the Quantity-Frequency-Variability Index (Cahalan, Cisin, & Crossley, 1969);
10. Any contraindications for MRI studies, e.g. severe claustrophobia, weight above 350 lb maximum allowed by MRI scanner, pregnancy;
11. Participation in another concurrent clinical trial;
12. Inability or unwillingness of individual or legal representative to give written informed consent;

4.3 Study Enrollment Procedures

Recruitment strategies. (1) We will recruit participant in collaboration with the NIA-funded Stanford Alzheimer's Disease Research Center (ADRC) and the California-funded Stanford-VA AD Center. The two centers will enable us to minimize screen fails by referring participants who are likely to meet the study's eligibility criteria. The ADRC and California AD center both have ongoing outreach efforts in place to recruit participants of diverse ethnic and racial backgrounds. (2) Participants will also be recruited from local clinics and physicians. We estimate that the Study Coordinator will conduct 3 screens for every 1 that is eligible for randomization.

To augment the AD Centers' outreach efforts to older, ethnically diverse individuals, we have budgeted for direct-mail advertising that will be targeted to older ethnically diverse residents. Local area marketing companies have lists of individuals by age, by minority status, and by geographical area. Our collaborators at both Centers have found that these IRB-approved postcards are one of the most effective outreach strategies. More general advertising will include IRB-approved flyers posted throughout the Stanford campus, VAPAHCs and AD Center newsletters. Interested respondents will learn more about the study during a telephone interview. If the respondent has never had a MCI/dementia work-up, they will be invited to undergo the rTMS study's screening evaluation at the NIA

ADRC or the California AD Center to obtain a consensus diagnosis and provide educational services to the participant and family.

Overview of consent procedures. Our IRB approval includes a waiver of individual HIPAA authorization for recruitment and a waiver of documentation of consent for telephone pre-screening. Before any in-person screening procedure is performed, written informed consent will be obtained. A single consent form describes both the screening and study procedures.

Enough time will be allowed for the potential participant to make an informed decision, including time to discuss the study with the researchers and ask any questions they may have. If the prospective participant lacks adequate decision-making capacity, a designated legal representative will need to sign the form prior to the participant undergoing screening or other study procedures. Prospective participants will need to co-sign the consent form to indicate assent. Consent procedures are described more fully in Sections 11.1 and 11.2.

Documentation of eligibility and decision to enroll. A Phone Screening Log will be used to record information on each candidate who is pre-screened by telephone prior to scheduling Visit 1, the in-person screening visit. For each candidate screened in person, two forms will be completed to document eligibility and the participant's decision to enroll:

- The **Inclusion-Exclusion Form** will document study eligibility and reasons for ineligibility.
- The **Enrollment and Randomization Form** will document eligibility as a binary Y/N outcome. The form will also have a check-box variable for recording why an eligible candidate was not enrolled.

Randomization. Participants who meet all criteria for enrollment will be randomized in a 2:1 ratio to double-blind active treatment or sham at Baseline. Within the active and sham groups, subjects will be randomized in a 1:1 ratio to the two unmasked cortical sites. The method of random assignment to treatment (active vs. sham) and to cortical site (DLPFC vs LPC) will be determined by a computer-generated random sequence as explained in "Treatment Assignment Procedures 9.2.1."

For the purposes of the Data Analyses, there are 3 equally sized treatment groups of interest in this randomized trial:

- (1) one-third of subjects will receive active DLPFC;
- (2) one-third of subjects will receive active LPC; and
- (3) one-third of subjects will receive sham (sham DLPFC and sham LPC are combined).

5 STUDY INTERVENTIONS

5.1 Intervention Device

Briefly, the TMS device system used in this study is comprised of the following components: MagPro X100 magnetic stimulator, the C-B60 coil (for MT determination), Coil Cooler unit, and motorized treatment chair. These are the major components of the MagVita TMS Therapy system, which is FDA cleared to market for the treatment of drug resistant Major Depressive Disorder.

For this double-blind controlled trial, the TMS Therapy System will be configured with three additional research components: a Coil Cool-B65 A/P (Active & Sham figure-of-eight coil), a TMS Sham Noise generator (for masking any difference in sound between real and sham), and a Localite TMS Navigator Spectra Edition system (for fMRI-guided placement of the rTMS coil).

5.2 Schedule and Procedures for Administering the Study Intervention

Schedule. The intervention will be administered as 20 weekday sessions during a period of 2 to 4 weeks, depending on scheduling constraints. Typically, a participant will have a morning session and an afternoon session. At the study physician's discretion and if the participant requests, up to three rTMS sessions can be scheduled per day with at least a one-hour interval between sessions.

Intervention sessions are scheduled as a 1-hour blocks, to allow time for late arrivals, for assessments of adverse effects, and for the 25-minute rTMS intervention. The intervention will be administered in outpatient clinic setting. In all, the participant will receive a total of 20 rTMS sessions.

Procedures for administering the rTMS Intervention

1. Motor Threshold Determination. Prior to administering the intervention, the participant's right and left motor threshold (MT) will be measured to standardize the stimulation intensity to be 120% of resting MT, i.e. $1.2 \times \text{MT}$. The 120% intensity will be specific to the MT of each hemisphere. The TMS Operator will determine the left MT at the end the screening visit, and the right MT at the beginning of Session 1 of the Intervention Phase. The TMS Operator will record the right and left MTs—and the corresponding stimulation intensities equal to 120% of right and left MT—on the participant's TMS Intervention Log (described in Section 6.2.3). The participant's right MT will also be recorded within the TMS system in association with the participant's randomization treatment number. (The device software allows for one MT to be saved per participant.)

Left and right hemisphere MT will be determined using electromyographic measurement (EMG) of the resting contralateral thumb (abductor pollicis brevis) using a mathematical algorithm (Maximum-Likelihood Strategy using Parameter Estimation by Sequential Testing; MLS-PEST) that efficiently and reproducibly arrives at the participant's MTs. As explained in the appended TMS Operator manual (Appendix IV. "TMS Quick Guide and TMS Operator's Manual of Procedures"), adapted from the CSP #556 Study Protocol ([name], Fairchild, & George, 2015, November), the EMG and MLS-PEST features are incorporated within the TMS device and software. If the screening MT is so high that the TMS system lacks capability to deliver rTMS at an intensity of 120% MT, the participant will not be eligible to enroll in the study. Fewer than five percent of participants are expected to be ineligible due to an excessively high MT (see Table 2 of George et al., (2010) for a large-sample distribution of MT values). The remainder of this section gives an outline of the basic procedures for administering rTMS:

2. Neuronavigation to guide placement of the coil. The placement of the coil will be individualized to each subject, using the subject's MRI data collected at the Baseline visit. By using neuronavigation, we aim to optimize subjects' clinical responses (Bashir, Edwards, & Pascual-Leone, 2011; Fox, Buckner, White, Greicius, & Pascual-Leone, 2012; Fox, Liu, & Pascual-Leone, 2013), irrespective of whether the subject is assigned to DLPFC or LPC stimulation.

As discussed in the grant application, multiple sessions of rTMS, when applied to the DLPFC or LPC, can ultimately change DLPFC:PPC connectivity and LPC:PPC connectivity, respectively in TMRDD (Liston et al., 2014) and healthy young adults (J. X. Wang et al., 2014). Regarding aMCI, the most significant x , y , z coordinates of abnormal functional connectivity appear to be located near MNI coordinate: $x = 6$, $y = -52$, $z = 16$, located in the PCC bilaterally. This coordinate was derived through an ALE meta-analysis of 21 rs-fMRI studies comparing aMCI participants to healthy older control participants (Lau et al., 2016). Therefore, in the present study, each subject's MRI data and a frameless stereotactic neuronavigation system will be used to position the coil where it is most likely to ultimately target the medial PCC, given evidence that this hub-like region of the brain is most consistently abnormal in aMCI.

The present study's procedures for neuronavigation will be performed in consultation with [name] and [name] of Stanford University School of Medicine. The general methods, which are based on prior work (J. X. Wang & Voss, 2015), are outlined in the grant submission, Section C.2.d.4 and in Appendix VIII. "Resting-state functional MRI Methods"). Briefly, the first step is to generate a seed-based connectivity map for each subject, using the subject's rs-fMRI Baseline data. In this step, the fMRI timeseries of the bilateral PCC region will be extracted as the seeds. Next, timeseries analyses will be used to locate bilateral LPC or bilateral DLPFC cortical targets, depending which of the two cortical site the subject has been randomly assigned to. If the fMRI data are too noisy due to excessive head motion, large framewise displacement, and/or low temporal signal-to-noise ratio, then the T1-weighted anatomical image will be used as a fallback. Review of data quality and selection of stimulation locations for individual subjects will be done in collaboration with [name]. [name] image-processing pipeline and connectivity mapping procedures are currently being used in four ongoing rTMS projects at Stanford, each involving unique diagnoses or unique targets.

LPC: To locate the left and right LPC cortical stimulation sites, we will locate the clusters of voxels located within the left and right angular gyri (and near Brodmann Area (BA) 39/40) that show local maximum connectivity (i.e. are positively correlated) with the PCC seeds. The left cluster should also lie within a 15-mm radius of MNI coordinate: $x = -47$, $y = -68$, $z = 36$; this coordinate is the peak location, across subjects, in the rTMS experiment that stimulated the left LPC to improve memory (J. X. Wang et al., 2014).

DLPFC: To locate the left and right DLPFC sites for stimulation, we will locate the clusters of voxels within left and right prefrontal gyri (near the juncture of BAs 9 and 46) that show local maximum negative connectivity (i.e. are inversely correlated) with the PCC seeds. The left cluster within the DLPFC should also lie within a 15-mm radius of the peak MNI coordinate ($x = -38$, $y = 44$, $z = 26$), which was found to be predictive of how effective rTMS was in treating clinical depression (Fox et al., 2012). This coordinate is also near the peak active cluster in fMRI studies of working memory in MDD (Fitzgerald et al., 2006), and shows significant inverse correlations with the PCC in resting-state fMRI (Greicius, Krasnow, Reiss, & Menon, 2003).

Following localization of the stimulation site (LPC or DLPFC), the bilateral locations for that subject will be marked in stereotactic space, transformed into original MRI space, and overlaid onto the structural MRI to aid in positioning the coil for the intervention. These locations will be marked on the subject's cap. Once the locations are marked, a coil template will be placed over each location to mark the location on the cap where the edge of the coil should be. As described in the TMS Operator manual (Appendix IV), cap fitting

and marking provides a way of reproducibly delivering rTMS across multiple intervention sessions.

3. Procedures for each intervention session. Except for positioning the rTMS coil over the assigned cortical site, the intervention procedures are identical for all treatment groups. The TMS Operator manual (Appendix IV) lists, step by step, the procedures for safety screening, for operating the rTMS device, placing scalp electrodes (see also Section 5.3 below), cap repositioning, positioning the participant for comfort and stable head position, delivering the treatment and monitoring for safety and tolerance to the procedure. The TMS Operator will manually set the amplitude to equal 1.2 times the MT of the to-be-stimulated hemisphere. For example, if the right MT = 65 and the left MT= 70, then the TMS Operator will manually set the amplitude to 78 (1.2 x 65) to stimulate the right, and to 84 (1.2 x 70) to stimulate the left.

As in Ahmed et al (Ahmed et al., 2012), rTMS will be applied over the right hemisphere first, immediately followed by rTMS over the left hemisphere. Rabey et al. (2013) also used a R, L order for the two bilateral regions. In both studies, all participants will receive the same order. It is beyond the scope of this study to investigate order effects. Given the absence of *a priori* data on this point, this study will follow the methods of the two prior studies (Ahmed et al., 2012; Rabey et al., 2013) and stimulate the right, immediately followed by the left.

TMS Stimulation Parameters for the active DLPFC and active LPC rTMS intervention groups will be: 10 Hz, 4-second train duration and 11-second inter-train interval. During each session, 2,000 pulses will be applied for each hemisphere (for a total of 4,000 pulses per session). These parameters will be pre-programmed in the device at the outset of the clinical trial, before the TMS operator begins administering the intervention.

Modifications and supportive care in case of difficulty tolerating the intervention. As noted previously, headache, scalp discomfort at the site of stimulation are relatively common, although tolerance to these adverse effects generally develops over the first 5 to 10 sessions of TMS therapy (Perera et al., 2016). Should a headache or site discomfort occur, these symptoms are expected to be self-treated, e.g. with ibuprofen. Discomfort can vary depending on intensity and location. For better tolerability, intensity can be ramped up from 80% to 120% during the first two sessions, and study staff may be able to move the coil position slightly if dental pain occurs.

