6.1 Schedule of Assessments

On the following page, **Table 2** lists the study assessments and their timing during the Pre-Treatment, Treatment, and Follow-up phases of the study. Following Table 2, we list each assessment that will be performed during these phases.

Table 2. Schedule of Assessments

	Pre-Treatment Phase		Treatment Phase			Follow-up Phase		
Visit Description	In-person Screening	Randomization & Baseline	Sessions 1-10	Sessions 11-20	Make-up sessions allowed through Day 37	Immediate Post-Tx	3-Month Post-Tx	6-Month Post-Tx
Visit Number	1	2	3-7	8-12		13	14	15
Timeline	Days -42 to -35	Day 0	Days 7-11	Days 14-18	Days 21-37	7 ± 3 days after S20	90 ± 14 days after S20	180 ± 14 days after S20
Informed Consent Form	X							
Demographics	X							
Vital Signs	X		X	X	X		X	X
Cognitive Change Index; MMSE, Logical Memory I	X							
CDR (Subject and SP)	X							
GDS, ETOH Questionnaire, Logical Memory II	X							
Medical, Psychiatric & Seizure Hx; Hach; PE/NE; Diagnostic Summary	X							
Concomitant Medications	X	X	X	X	X	X	X	X
MRI and rTMS Safety forms; Motor Threshold (MT)	Safety & Left MT	Safety	Safety & Right MT	Safety	Safety	Safety		
Inclusion/Exclusion Criteria	X							
Enrollment/Randomization		X						
MRI scan		X				X		
CVLT-II and Secondary Behavioral Assessments		X				X	X	X
Blood Sample (Genomic DNA and BDNF Biomarkers)			Session 1 DNA & BDNF		Session 20 BDNF only			
rTMS Intervention Log			X	X	X	X	X	
Adverse Events		X	X	X	X	X	X	X

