6.2.3 Intervention Visits (Visits 3 – 12)

A participant will receive a total of 20 rTMS intervention sessions within a period of 2 to 2.5 weeks, depending on scheduling constraints. Typically, a participant will have a morning session and an afternoon session during a one-day clinical visit. Accordingly, 2

intervention sessions are recorded as a single “visit” and the visits are numbered from Visits 3 through Visit 12.

The first intervention session (Visit 3) needs to take place during a window of 7 ± 3 days after the completion of the Baseline assessments. An Intervention session is scheduled as a 1-hour block to allow time for late arrivals, assessment of adverse effects, and for the 20-minute rTMS intervention. At the study physician’s discretion and if the participant requests, up to three rTMS sessions can be scheduled per day with at least one hour between sessions.

To be fully adherent, the participant should complete 20 sessions within 30 calendar days.

The following assessments and procedures will be performed at the Intervention Visits:

First Intervention Session (am, Visit 3: *Overnight fasting is necessary*)

- Concomitant Medications (update of previously recorded medications)
- Adverse Events (to capture a new or a worsening pre-existing condition)
- Vital Signs
- Fasting Blood Sample (Genetic and BDNF Biomarkers), followed by breakfast
- rTMS Safety Questionnaire
- Motor Threshold Determination (Right Hemisphere), as described in Section 5.2*
- rTMS Intervention Log
- Administration of study intervention, as described in Section 5.2
 - * *Motor thresholds will be rechecked at the study physician’s direction at subsequent intervention sessions in the event a change in medication or a change in sleep pattern is reported by the participant and/or study partner. If a participant’s subsequent MT is greater than the capacity of the TMS device, the subject will be treated at the maximum device capacity and tracked as such.*

Second Intervention Session (pm, Visit 3)

- Concomitant Medications
- Adverse Events
- rTMS Safety Questionnaire if more than 24 hours since the previous
- rTMS Intervention Log
- Administration of the study intervention

Intervention Sessions 3-18 (Visits 4 – 11)

- Concomitant Medications
- Adverse Events
- Vital Signs
- rTMS Safety Questionnaire
- rTMS Intervention Log
- Administration of the study intervention

Intervention Session 19 (am, Visit 12: *Overnight fasting is necessary*)

- Concomitant Medications

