9.5 Data Analyses

9.5.1. Primary Hypothesis Testing

- Analysis: Test the hypothesis that active rTMS (to either stimulation site) is superior to sham in improving memory performance, as observed at the immediate post-treatment visit.
- Method: Analysis of Covariance (ANCOVA)
- Population: Intention-to-treat (ITT), defined as all randomized patients who started at least 1 treatment session.
- Independent variable: rTMS Treatment group
 - ANCOVA 1: active DLPFC vs sham
 - ANCOVA 2: active LPC vs sham
- Dependent variable: Primary outcome, i.e. CVLT-II Trials 1-5 Total raw score at Visit 13
- Covariate: CVLT-II Trials 1-5 Total raw score at Baseline, i.e. Visit 2
- Results will be presented as n, mean and standard deviation of CVLT-II (Total Trials 1-5) scores at baseline and post-treatment. ANCOVA model parameters with estimates will be provided.
- The two tests of treatment effects will be conducted at a 2-sided alpha level of 0.05, adjusted for two tests; 2-sided confidence intervals will be displayed with a 95% confidence level.

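### Motor-threshold eligibility is settled on the left hemisphere only; the right is first measured after randomisation, so an unobtainable right threshold is found too late

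*Combined protocol and SAP*

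**What the plan says.** Inclusion criterion 5 (Section 4.1) requires "Ability to obtain a motor threshold, determined during the screening process". It names no hemisphere.

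Section 5.2 splits the two measurements. For one side, "The TMS Operator will determine the left MT at the end the screening visit". The other side waits until treatment begins, with the plan scheduling "the right MT at the beginning of Session 1 of the Intervention Phase". The screening column of Table 2 (Section 6.1) agrees, reading "Safety & Left MT", and the screening list in Section 6.2.1 also names only the left hemisphere.

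The device-capacity exclusion in Section 5.2 opens "If the screening MT is so high that the TMS system lacks capability to deliver rTMS at an intensity of 120% MT". It therefore applies to the left reading. The same section expects fewer than 5% of participants to be ineligible for a very high MT.

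For later readings, a footnote to the Session 1 right-MT line in Section 6.2.3 first describes rechecks at later sessions. It then says that if a subsequent MT exceeds the device's capacity, "the subject will be treated at the maximum device capacity and tracked as such".

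The primary analysis population (Section 9.5.1) is called intention-to-treat (ITT) and defined as "all randomized patients who started at least 1 treatment session". Section 8.3 provides replacements only for events before randomisation.

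**The concern.** Intensity is set separately for each hemisphere and the right is stimulated first, so a usable right MT is needed before the first session can be delivered as written. The plan checks this only after the participant has been randomised, scanned and mapped for coil placement.

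A failure on the right then has no visible route through the plan. If the right MT cannot be obtained, the participant may never start a session. That person would fall outside the primary analysis set although randomised, and would not be replaced. If the right MT is above device capacity, the text can be read two ways. At stake are a few avoidable exclusions after randomisation and some precision in a trial of 33 per arm.

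**Working it through.** **Sequence of events**

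1. Screening (Visit 1): left MT obtained; criterion 5 and the capacity rule applied to it (Sections 4.1, 5.2, 6.2.1, Table 2).
2. Randomisation: at least 14 days before the intervention (Section 6.2.2). Sections 4.3 and 8.3 place it differently relative to Baseline, but every version puts it before Session 1.
3. Session 1 (Visit 3): right MT first attempted, then stimulation, right side first (Sections 5.2, 6.2.3).
4. Analysis: randomised and at least one session started (Section 9.5.1).

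**What the text gives for each outcome of the first right reading**

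- *Obtained, within capacity:* treatment proceeds.
- *Obtained, above capacity:* the Section 6.2.3 footnote keeps the participant on treatment if a subsequent MT means any reading after screening. If it means only a recheck, no rule is stated. On the left at screening, the same finding would have excluded the person.
- *Not obtainable:* no rule in the available text. Section 5.2 places MT measurement before the intervention is administered, so a failed attempt may not count as a started session. Section 6.2.5 also permits termination if investigators judge an enrolled participant ineligible.

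**The plan's own power figure**

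Inputs from Section 9.2: d = 0.8, 80% power, two-sided 5% with a penalty for two tests. I take the penalty as Bonferroni, alpha = 0.025 per test (assumption; the method is not named). For n per arm, use a two-sample t-test with df = 2n − 2 and noncentrality d·√(n/2).

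- n = 31: noncentrality 0.8 × √15.5 = 3.150, df 60, critical value 2.299, power **80.0%**. This is the smallest n that reaches 80%.
- 31 / (1 − 0.06) = 32.98, so 33 per arm, the stated number.
- n = 33: noncentrality 0.8 × √16.5 = 3.250, df 64, critical value 2.295, power **82.7%**.

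The stated 80% is thus reproduced if 33 already allows for the 6% attrition cited from a previous trial. The plan does not say that it does, so both baselines are shown.

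**Effect of right-side losses**

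Let p be the proportion lost because of the right MT. The documents give no value for p after an acceptable left MT. I assume 0 to 5%; the upper end borrows the plan's ceiling for a high screening MT, which is a different event. Evaluable n per arm is 33(1 − p), or 33 × 0.94 × (1 − p) with 6% attrition.

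| p | Lost of 99 | n per arm | Power | n per arm, 6% attrition | Power | Chance of at least one case, 1 − (1 − p)^99 |
|---|---|---|---|---|---|---|
| 0 | 0 | 33.00 | 82.7% | 31.02 | 80.0% | 0% |
| 1% | 1.0 | 32.67 | 82.3% | 30.71 | 79.6% | 63% |
| 2.5% | 2.5 | 32.17 | 81.7% | 30.24 | 78.9% | 92% |
| 5% | 5.0 | 31.35 | 80.5% | 29.47 | 77.7% | 99% |

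The largest cost is 82.7 − 80.5 = 2.2 points without other attrition, or 80.0 − 77.7 = 2.3 points with it.

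**The case against.** **High right MT.** A reader might infer that ineligible participants are randomised and then excluded. The documents do not support that. Criterion 5 speaks of a single threshold and the capacity rule of the screening MT, so no written rule makes a high right MT an ineligibility. The Section 6.2.3 footnote hangs on the Session 1 right-MT line, so it may well cover that first reading. Such a participant would be treated, start a session and stay in the analysis. This objection stands: exclusion is a clear risk only for an unobtainable right MT, or if investigators terminate participation.

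**Size.** A reader might also carry the under-5% figure straight over as the loss, or suppose two further losses in every arm. That figure concerns a high MT, not an unobtainable one, and everyone randomised has already passed on the left. Two per arm would be 6 people, more than the assumed ceiling of about 5 of 99. This stands, and it is why 77.7% is the floor here.

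**Power reserve.** The primary test is ANCOVA on the baseline score, and Section 9.1 cites retest reliability above 0.75. If d = 0.8 is in raw standard deviations (assumption) and the correlation is 0.75, the effective d is 0.8/√(1 − 0.5625) = 1.21. Power is then 99.5% at 33 per arm and 98.9% at 29.47. The plan does not say which standard deviation d refers to, so the t-test figures are the conservative case. It would be wrong to say that the trial has no power to spare.

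**Bias.** The right MT is measured the same way in every arm, before any stimulation, with active and sham masked. Loss should not differ between active and sham. The operator does know the cortical site, so a site-related difference cannot be ruled out, but nothing points to one. Section 9.2 also promises sensitivity analyses that include baselined participants with missing outcomes. These soften the exclusion but do not change the primary set.

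**Rules elsewhere.** Section 5.2 refers MT procedures to the operator manual in Appendix IV, which was not available to this review. It may say what to do when a right MT cannot be obtained. The timing gap would remain.

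**Conclusion.** The point holds in a limited form. Whether an MT can be obtained is known before randomisation for only one of the two treated hemispheres. A participant with an unobtainable right MT could be randomised, start no session and leave the primary analysis without replacement. For an over-capacity right MT, the text is ambiguous rather than exclusionary.

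The size is small: under the assumed 0 to 5% range, at most about 2 percentage points of power. This rests on the Bonferroni reading, an unadjusted t-test and every right-side failure being lost, the last of which overstates the effect if the footnote retains over-capacity cases. The harm is lost precision and a departure from analysing everyone randomised, not a bias of active against sham. It is worth correcting because the remedy is cheap, not because the primary result is threatened.

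**What to change.** Take the right MT reading at the screening visit alongside the left, so that whether an MT can be obtained is known for both hemispheres before randomisation. The Session 1 reading can remain.

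Reconcile Section 4.1 item 5, Section 5.2, Table 2 and Section 6.2.3. State which hemisphere or hemispheres the criterion and the capacity rule cover, and whether a subsequent MT includes the first right reading or only rechecks. What those rules should be, and any intensity or capacity limit, is for the investigators to decide.

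The cost is a few more minutes per screenee with the same operator, device and method, and possibly a few more screen failures. Section 4.3 expects three screens for each eligible participant, so the extra time also falls on people who will not be randomised.
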